2.1. Study Rationale

The purpose of the assessment study is to verify that the AIDAVA prototype virtual assistant meets the objective set for this device at the onset of the project.

- 1. Improve the quality, FAIRness, and portability of heterogeneous, Personal Health Data (PHD)
- 2. Increase value and reusability of PHD through integration and semantic enrichment within a common standard representation called the Personal Health Knowledge Graph (PHKG).

⁷ By "*data curation & publishing*" we mean the integration, harmonisation and quality enhancement (curation) and the transformation into a target format (publishing) of multimodal data, collected from various sources, to make it more usable by humans and machines.

⁸ Health Data Intermediaries are emerging organisations, regulated under the European Data Governance Act (DGA), enabling personal health data sharing on behalf of each consenting patient.

- 3. Optimise the data curation & publishing process.
- 4. Ensure compliance with EU ethical & data privacy requirements when processing personal data.
- Demonstrate the value of the developed novel tools for more effective treatment (Use Case 1 breast cancer registries federated across hospitals) and for preventive care (Use Case 2 longitudinal health record of cardiovascular patients at risk of sudden cardiac arrest).

2.2. Background

The AIDAVA virtual assistant prototype developed during the project will be deployed in a secure testing environment (see light green box below) within the 3 participating hospitals; each hospital will be working with a dedicated Health Data Intermediary (orange box on the left).

The primary objective is to support patients and expert curators⁹ in managing the patient longitudinal health record, and to allow patients to visualise their record. The secondary objective is to demonstrate that interoperable and reusable longitudinal health records can be reused (with consent of the patient) to effectively support clinical care and clinical research.

Figure 3. Components of the AIDAVA prototype and data flows

- Flows in greens represent internal flows within AIDAVA (see below)
- Flow and bullet in yellow represent external flows to AIDAVA, subject to Data Sharing/Processing Agreement with Data Transfer Specifications (see Section 11.4 on Data Protection)

Patients and data curators are expected to work through the following steps.

• Step 1. Ingestion. The patient - or data curator working as deputy of the patient - identifies data sources from the hospital EHR and from the patient HDI, and requests transfer of their

⁹ See definition in Study Population - Section 5.2
personal data from these data sources into the AIDAVA TEMP DATA STORE available within the hospital testing environment. These data are stored in their original format. Extraction from the data sources can be done with the support of the local registry steward, or automated whenever possible; this will be further specified in the Data Transfer Agreements signed between the Health Data Intermediaries (HDI-s), managing the non-hospital data of the patient, and the hospital.

- Step 2. Curation. The patient requests the AIDAVA virtual assistant to transform, integrate, potentially correct, and complete ingested data to generate a standardised representation of its individual's health record, the Personalised Health Knowledge Graph (PHKG). The AIDAVA virtual assistant will maximise automation in curating the data by orchestrating execution of relevant data curation tools for each curation step, and requesting input only when needed from the patient at their level of health and digital literacy or from the data curator when it is expected that the patient will not be able to answer.
- Step 3. Publishing. The HDI responsible for managing the data of a patient, specifies the data that should be extracted from the PHKG to support visualisation and potential other processing through the selected 3rd party app. At the moment of writing the document, we intend to extract the data elements supporting the International Patient Summary (IPS) based on the HL7 FHIR profile. The specification of the extract can be done once and executed many times, whenever there is a refresh of the data sources and the PHKG. Once the extract's specification is confirmed, the AIDAVA virtual assistant extracts the data from the PHKG, performs the needed transformation to generate the target format required and transfers the data to the HDI.
- Step 4. Use. The 3rd party application, selected by the respective HDIs, will display the patient data and support querying. The fact that the applications used for visualisation are different, while working on the same underlying PHKG structure will demonstrate interoperability and reuse of the underlying data.

Clinical care providers and clinical researchers also benefit from the PHKGs curated by the patient and/or the data curator.

For breast cancer clinical researchers.

• Step 3a. Publishing data to simulate delivery of a "EU" Breast Cancer registry. To simulate how a tool like the AIDAVA prototype can support delivery and maintenance of a "EU" wide Breast Cancer registry, a list of data elements to be extracted from each participating centre has been established by the breast cancer specialists (see ref). This list is a first draft to demonstrate the concept; to deliver a real EU Breast Cancer registry, the list should be updated after validation by an international team of breast cancer specialists.

The AIDAVA prototype will generate the same data extract - from heterogeneous data sources - in the specified format across the 3 participating sites.

• Step 4a. Analytics of the extract across different sites. To demonstrate interoperability of the resulting extracts, the prototype will execute a set of "federated" queries (see Section 3.2.1) i.e. queries run with local data across all 3 sites with consolidation of the results into one single answer. This enables the build a EU wide registry while avoiding transfer of data outside of the hospital.

For cardiovascular specialists, following patients.

• Step 3b. Publishing data to compute the SMART risk score . The AIDAVA Virtual assistant supports automatic extraction and transformation from the patient PHKG into the data

elements and format needed for computation of the SMART risk score (see Section 3.2.2). The prototype virtual assistant will generate the same data extract in the specified format across the 3 participating sites.

• Step 4b. Analytics of the extract across different sites. To demonstrate interoperability of the PHKG and of the resulting extracts, we will use the same SMART risk algorithm across the 3 sites and provide results to the cardiovascular specialists.

The fact that the system can generate 3 different extracts from the same PHKG (visualisation for the patient and potentially additional processing as specified in the HDI collaboration agreement, extract for breast cancer registry, extract to compute the SMART risk score), demonstrates a key principle of AIDAVA "curate once, use many times".

2.3 Benefit/Risk Assessment

Taking into account that the study is assessing a "software as a device" prototype system with no impact on clinical care or clinical research, the risks are limited while the anticipated benefits are major. The table below provides a list of benefits and risks for the different actors involved.

	Benefit	Risk
Patient (Breast Cancer and CVD)	 Manage/control their own data and are able to visualise and query their record Thanks to high quality health record, access to better clinical care (preventive and personalised medicine) Contribute to the greater good by sharing high quality data for research 	If data are not secured properly ¹⁰ , risk of fraudulent access to highly sensitive data (this risk will be mitigated when deploying the prototype) If the patient does not answer properly to a question of AIDAVA, this could introduce errors in the medical record (but there will full traceability of the information entered)
Expert data curator ¹¹	Decrease workload when preparing data sets for secondary use (registry or clinical care score)	Time to learn another system, with too much workload upfront Curator may introduce errors (does not answer properly to a question of AIDAVA), this could introduce errors in the curated record in AIDAVA (i.e. the personal health knowledge graph or PHKG) but the original record will NOT be modified and there will be full traceability of the information entered.
Breast Cancer Specialist (Use Case 1)	Faster and more efficient access to high quality data to support breast cancer research across EU	The risk that the curated data are not sufficient/of sufficient quality to make decisions (being mitigated by data quality module). Note: As the system is a prototype, it cannot be used for clinical decision making or as a

¹⁰ Each site will perform a Data Protection Impact Assessment; requirements for the prototype being developed include data security principles in alignment with GDPR and EU best practices.

¹¹ See definition in Study Population - Section 5.2

	Benefit	Risk
		decision support system for clinicians.
Cardiovascular Specialist (Use Case 2)	Faster and more efficient access to clinical score for their patients, supporting more effective monitoring	The risk that the curated data are not sufficient/of sufficient quality to make decisions (being mitigated by data quality module) Note: As the system is a prototype, it cannot be used for clinical decision making or as a decision support system for clinicians.

3. Objectives and Endpoints

3.1. Primary endpoints

The **primary objective** of the assessment study is to compare the acceptance and the performance of the AIDAVA prototype versus existing practice, and between the 2 versions of the prototype. To this end, we propose to measure the following endpoints that will be recorded across sites.

Objective	Primary Endpoints
Metric 1. Evaluate acceptance by end users	Metric definition: Structured questionnaire (adapted from a System Usability Scale with additional questions such as I would recommend AIDAVA to my friend, colleague, or family member I am interested / ready to work with AIDAVA when available on the market I understand the purpose of data curation I am ready to spend the needed time to ensure proper data curation The curation process was perfect/acceptable/too long for me Measurement score (M1) through structured questionnaire (System Usability Scale - form) provided in REDCap
Metric 2. Measure	Metric definition
impact on workload for quality enhancement of data (including quality of the different curation tools)	 Compare time spent in curating data in G0 (current situation) G1 (generation 1 of the prototype) G2 (generation 2 of the prototype). Check the amount of data curated in the average time: are there more data being curated together with the ones needed to support the use case
	 Measurement For estimated time spent in curating (M2.1) User entry in dedicated "Curator form" (RedCap) For curators, when requesting an estimate for G0, it is important to ensure that curated data set have the same level of complexity as for G1 and G2 complexity: Extract a sample (synthetic data ?) to be curated including several data sources; Request existing registry stewards to provide a time to curate data up to insertion into registry (M2.2) System check "active" time of user to answer a query Amount of additional data elements are curated automatically computed (M2.3) How many data elements have been curated automatically by the systems (M2.4) How many data elements have required human interventions and been successful answered by the patients (i.e. answer provided to the question)

Objective	Primary Endpoints
	 (M2.5) How many data elements have required human interventions can not be answered by the patients and are sent to the curators (M2.6) How many data elements send to the curators did not get appropriate answer to finish the curation process
Metric 3. Measure quality of data resulting from the data curation & publishing - in terms of their interoperability and reusability	 Metric definition: Data quality score measuring components related to the quality of the personal health knowledge graph and supporting its re-use. This includes dimensions such as volume (number of data items curated), completeness (number of missing items), consistency (number of consistency checks that fail), availability of context information (metadata).
	 Measurement: automatically computed by system at G1 and G2: System computes scores automatically ; formula are being defined in D4.6/Task 4.2 (due date Feb 2024)
Metric 4. Assess the quality/quantity of concepts that can be extracted from clinical narratives with different technologies	 Metric definition: Computed quality of the NLP concept extraction against the manually annotated data ("gold standard") Precision (M4.1): fraction of correct gold standard instances among the retrieved instances Recall (M4.2): fraction of the gold standard concepts that are successfully extracted
	 Measurement 0. Requires a manually annotated gold standard 1. Measure at G0 (current situation): measure # of concepts extracted for registry, manually – in limited time frame (few minutes) 2. Measure at G1 and G2: Precision/Recall for three different NLP systems a. The minimal-effort translation-based system developed for G1 b. The tools with novel DL models developed for G2 c. Measuring generalisation ability to new languages (at G2) The expected outcome is that (b) > (c) > (a). We will measure how well models trained of any two of the three languages (German, Dutch, Estonian) can generalise to the third language as a proxy for how well the overall system can adapt to new languages.

3.2. Secondary endpoints

The **secondary objective** of the clinical evaluation study is to assess the value of a tool such as AIDAVA to support reuse of data for clinical research, by delivering a EU wide federated clinical registry, and for clinical care, by providing useful information to the treating physicians while decreasing their workload (time saving). The secondary endpoints will be recorded in each site in a dedicated spreadsheet (see model in Section 10.6) shared across sites.

3.2.1 Breast Cancer Use case

Objective. The measures described below have no scientific rationale; their intent is to demonstrate that heterogenous data curated across different sites and different countries have been "FAIRified" thanks to AIDAVA i.e. they can produce comparable - and interoperable - data sets across different sites, supporting de facto delivery of a federated cross site registry.

The metrics will be based on assessing time needed and accuracy for 3 queries to be performed on the BC registry. **Important to note that the queries need to have a consolidated answer ACROSS sites** to demonstrate interoperability.

Queries	Technical Specification of the query (all codes are SNOMED code
	matched with the list of Data Elements in the BC registry)
Metric 1: Percentage of patients	BC1 = P2/P1 WHERE
- across sites -  treated with	
breast conserving therapy and	P1 = Total number of patients 404684003 Clinical finding (finding)
whole breast radiotherapy that	WITH 64368001 Excision of part of breast (procedure)
receive a boost to the tumour	AND 428923005 Radiotherapy to breast (procedure)
bed.	
	P2 = Total number of patients 404684003 Clinical finding (finding)
	WITH 64368001 Excision of part of breast (procedure)
	AND 428923005 Radiotherapy to breast (procedure)
	AND 445232009 Boost radiation therapy (procedure)
Metric 2: Percentage of patients	BC2 = P2/P1 WHERE
- across sites - undergoing	
breast surgery and	P1 = Total number of patients 404684003 Clinical finding (finding)
radiotherapy, without adjuvant	WITH 392090004 Operation on breast (procedure)
chemotherapy AND with time	AND 108290001 Radiotherapy (procedure)
between surgery and	WITHOUT 367336001 Chemotherapy (procedure)
radiotherapy > 8 weeks	BEGINTIME OF (367336001 Chemotherapy (procedure))
	>=
	BEGINTIME OF (392090004 Operation on breast
	(procedure))
	P2 = Total number of patients 404684003 Clinical finding (finding)
	WITH 392090004 Operation on breast (procedure)
	AND 108290001 Radiotherapy (procedure)
	WITHOUT 367336001 [Chemotherapy (procedure)]
	BEGINTIME OF (367336001 Chemotherapy (procedure))
	>=
	BEGINTIME OF (392090004 Operation on breast
	(procedure)))
	AND TIME OF 108290001 kadiotherapy (procedure)
	7- TIME of (108290001 Radiotherapy (procedure) + 8 weeks)
Metric 3: Percentage of in	BC3 = P2/P1 WHERE

Queries	Technical Specification of the query (all codes are SNOMED code matched with the list of Data Elements in the BC registry)
patients - across sites - receiving nodal radiotherapy out of any radiotherapy	P1 = Total number of patients 404684003 Clinical finding (finding) WITH 108290001 Radiotherapy (procedure)
	P2 = Total number of patients 404684003 Clinical finding (finding) WITH 168522007 Radiotherapy for lymphatic irradiation (procedure)

The actual metrics/ endpoints can then be defined as follows.

Objective	(Secondary) end point	
Metric 1. Time required to compute different queries of interest within the BC registry	Metric definition: Time to have an answer to the 3 queries (BC1, BC2 and BC3) with information from the BC registry - across sites Note 1: should include time of the BC specialist and supporting team (spending most of the time) Note2: should be the same between G1 and G2)	
	 Measurement: TBCx. User entry in dedicated "Data User form" (RedCap) for each of the queries 	
Metric 2: Accuracy of measurement	Metric definition: accuracy of the answer for each of the parameter between AIDAVA and the BC specialist	
	 Measurement: For each of the query (BC1, BC2, BC3), HBCx. Ask the value from the human (through RedCap Form) ABCx: get the value computed by AIDAVA ACCx: accuracy of calculation by AIDAVA (ABCx) compared to BC specialist (HBCx) 	

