Metric 3. Measure quality of data resulting from the data curation & publishing - in terms of their interoperability and reusability	 Score (computed automatically) measuring components related to volume (number of data items curated) completeness (number of missing items) consistency (number of consistency checks that fail) availability of context information (metadata)
Metric 4. Assess the quality/quantity of concepts that can be extracted from clinical narratives with different technologies	 Precision (M4.1): fraction of correct gold standard instances among the retrieved instances Recall (M4.2): fraction of the gold standard concepts that are successfully extracted

Secondary - Breast Cancer use case	
Demonstrate the ability to perform the exact same computation in each site and to consolidate across sites, showing interoperability of data curated from different sources and ability to build a federated registry.	 Metric 1: Percentage of patients - across sites - treated with breast conserving therapy and whole breast radiotherapy that receive a boost to the tumour bed. Metric 2: In patients - across sites - undergoing surgery and radiotherapy, without adjuvant chemotherapy: % of patients with time between surgery and radiotherapy > 8 weeks. Metric 3: Percentage of In patients - across sites - receiving nodal radiotherapy out of any radiotherapy.
Secondary - Cardiovascular use case	
Demonstrate the value of having interoperable and reusable data in a standard format to provide information of value in clinical care - without additional burden to the physician	 Metric 1. Compare scoring time between AIDAVA and CVD experts Metric 2 . Compare scoring accuracy between AIDAVA and CVD experts

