Start neoadjuvant radiotherapy	108290001 Radiat oncology AND, radiotherapy (procedure)	ion 373847000 /OR Neo-adjuvant - intent (qualifier value)	Date	439272007 Date of procedure (observable entity) 413946009 Date treatment started (observable entity)	
Adjuvant radiotherapy	108290001 Radiat oncology AND, radiotherapy (procedure)	ion 373846009 Adjuvant - /OR intent (qualifier value)	- Yes No Unknown	373066001 Yes (qualifier value) 373067005 No (qualifier value) 261665006 Unknown (qualifier value)	
Target volume: Chest wall	428624002 Radiotherapy chest v (procedure)	to vall	Yes	373066001 Yes (qualifier value) 373067005 No (qualifier value)	
Target volume: Interpectoral nodes	168522007 Radiotherapy lymphatic irradiat (procedure)	for ion	Yes	373066001 Yes (qualifier value)	

Data Element	Variable SNOMED code + FSN	Variable alternative SNOMED codes	Permissible values	Values SNOMED code + FSN	Values alternative SNOMED code + FSN	(additional)
	245274001 Interpectoral lymph node group (body structure)		No	373067005 No (qualifier value)		
Target volume: Internal mammary nodes	168522007 Radiotherapy for lymphatic irradiation (procedure) 245282001 Internal mammary lymph node group (body structure)		Yes No	373066001 Yes (qualifier value) 373067005 No (qualifier value)		
Total dose prescribed	399077005 Prescribed external beam radiation therapy dose (observable entity)		Gy	229029004 Gray (qualifier value)		
Number of fractions to elective regions	445232009 Boostradiationtherapy(procedure) 410673009 Region(attribute) 103390000 Elective(qualifier value)	228862004 Number of fractions (observable entity)	Number	260299005 Number (qualifier value)		
If boost, Fraction dose boost	445565002 Total boost radiation dose delivered (observable entity)		Gy	229029004 Gray (qualifier value)		

Data Element	Variable SNOMED code + FSN	Variable alternative SNOMED codes	Permissible values	Values SNOMED code + FSN	Values alternative (additional) SNOMED code + FSN
If boost, Number of fractions to boost regions	445232009 Boost radiation therapy (procedure)	228862004 Number of fractions (observable entity)	Number	260299005 Number (qualifier value)	
Dermatitis	49084001 Dermatitis	108290001 Radiation	Yes	373066001 Yes (qualifier value)	
	caused by radiation (disorder)	oncology AND/OR radiotherapy	No	373067005 No (qualifier value)	
		(procedure)	Unknown	261665006 Unknown (qualifier value)	

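### The 8-week condition of breast cancer query BC2 compares radiotherapy with itself instead of with surgery, so AIDAVA's BC2 answer says nothing about curation quality

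*Protocol*

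**What the plan says.** **The metric in words.** The synopsis (section 1.1) asks for the percentage "of patients with time between surgery and radiotherapy > 8 weeks" among patients who had surgery and radiotherapy without adjuvant chemotherapy. Section 3.2.1 repeats the definition, ending in "radiotherapy > 8 weeks". The G0 data user form in section 10.3.4 describes the same interval.

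**The metric as specified.** In the technical column of section 3.2.1, BC2 = P2/P1. P1 requires breast surgery (392090004) and radiotherapy (108290001), with the chemotherapy exclusion. P2 adds a time condition. Its left side is "AND TIME OF 108290001 kadiotherapy (procedure" and its right side is "TIME of (108290001 Radiotherapy (procedure) + 8 weeks"; with the operator as the text reads, the latter is "7- TIME of (108290001 Radiotherapy (procedure) + 8 weeks".

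**How the answer is used.** Under sections 3.2.1 and 9.2, AIDAVA's value (ABCx) is compared with the specialist's (HBCx) to give accuracy ACCx. Hypothesis H2-BC in section 9.1 asks for accuracy of at least 90% in G1 and similar or better results in G2. Section 9.3 tests the G1-to-G2 difference in ACCx.

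**The registry list.** The table heading in section 3.2.1 says that the query codes are matched with the registry data elements, which section 10.5 lists. As read there, the only radiotherapy start date is "Start neoadjuvant radiotherapy". BC1's numerator uses "AND 445232009 Boost radiation therapy (procedure", and the element for the number of fractions to elective regions is coded "445232009 Boostradiationtherapy(procedure) 410673009 Region(attribute) 103390000 Elective(qualifier value".

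**The concern.** The wording needs two events, surgery and radiotherapy. The specification uses only one. A condition that sets the time of an event against the time of that same event plus 8 weeks carries no information about the delay after surgery. If the query is executed as specified, the answer is fixed before any data are curated.

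BC2 is one of three queries meant to show that data from different sites can be combined into one correct answer. If its result is set by the query text, a gap between AIDAVA and the specialist would be read as a curation failure, and agreement as a success. Neither reading would be justified. The G1-to-G2 comparison has the same problem, because both generations would run the same condition.

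**Working it through.** The plan states no numerical result for BC2, so there is no figure to reproduce. The check evaluates the condition itself.

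**Inputs.** Left operand: time of 108290001. Right operand: time of 108290001 + 8 weeks (56 days). Operator: garbled in the text; `>=` is assumed because the chemotherapy clause of the same query uses it and the wording says more than 8 weeks. Breast cancer patients: 45 (section 9.4). All must have had surgery and radiotherapy (section 5.2).

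**Step 1: evaluate the condition.** Let s be the surgery date and t the radiotherapy date. As written the test is t >= t + 56, which reduces to 0 >= 56. The worded metric is t > s + 56.

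| Gap t − s (days) | As written, `>=` or `>` | As written, `<=` | Surgery-based, `>=` | Surgery-based, `>` |
|---|---|---|---|---|
| 0, 14, 28, 55 | false | true | false | false |
| 56 | false | true | true | false |
| 57, 70, 120 | false | true | true | true |

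The written condition does not vary with the gap under any operator. With `>=` or `>`, P2 = 0 and BC2 = 0/P1 = 0% whenever P1 > 0. With `<=`, P2 = P1 and BC2 = 100%. The row at 56 days also shows that `>=` and the worded `>` differ at exactly 8 weeks.

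**Step 2: size of the distortion.** The protocol gives neither the share without adjuvant chemotherapy nor the share delayed. I assume 40–80% for the first and 10–50% for the second. P1 = 45 × share without chemotherapy; P2 = P1 × share delayed, rounded to whole patients.

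| P1 | P2 at 10% | P2 at 30% | P2 at 50% |
|---|---|---|---|
| 45 × 0.4 = 18 | 2 (11.1%) | 5 (27.8%) | 9 (50.0%) |
| 45 × 0.6 = 27 | 3 (11.1%) | 8 (29.6%) | 14 (51.9%) |
| 45 × 0.8 = 36 | 4 (11.1%) | 11 (30.6%) | 18 (50.0%) |

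The intended BC2 would be about 11% to 52%. The query as written gives 0% in every cell.

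**Step 3: effect on accuracy.** No formula for ACCx is given. If, for illustration, it were 100 minus the difference in percentage points, an answer of 0% would score 100 when the true value is 0%, 90 when it is 10%, and 70 when it is 30%. The 90% criterion would then be met or missed according to the true share of delayed patients, not the quality of the curated data.

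**Step 4: two radiotherapy records.** Section 10.5 places neoadjuvant and adjuvant radiotherapy under the same code. For a patient with records at day 0 and day 140, an engine that pairs different records finds 140 >= 0 + 56, which is true. Such a match measures the time between two radiotherapy courses, not the time since surgery.

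**The case against.** **It is a copying slip, with the right definition in the same table row.** This is true, and an attentive programmer may notice. The technical column is nevertheless what is to be implemented, and nothing elsewhere in the protocol corrects it. PDF reading can explain a wrong first letter and a broken operator, but not a complete radiotherapy code and label standing where the surgery code and label belong. The general software testing described in the deliverable's introduction does not name these queries.

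**The measures are a demonstration.** Section 3.2.1 says that they have no scientific rationale. Their stated aim is comparable answers across sites, and a constant cannot show that.

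**Several stronger readings are tempting, and the protocol does not support them.**

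- A reader might infer that the numerator is always empty at every site. The operator is garbled, a patient may hold two radiotherapy records, the reported answer is consolidated across sites, and BC2 is undefined where P1 = 0.
- A reader might infer that H2-BC cannot be met. Without an ACCx formula, or a statement whether 90% applies per query or overall, this does not follow; step 3 shows that a false pass is also possible. Only BC2 is affected by the wrong operand. The time and effort measures are not.
- A reader might infer that BC1 drifts to 100% because the boost code recurs in the elective-fractions element. That holds only if matching ignores the Region and Elective qualifiers, which is not specified.
- A reader might infer that the registry lacks an adjuvant radiotherapy start date and code 428923005. Section 10.5 as read has visibly lost content: the breast-conserving surgery row has no code, and two boost rows lack a parent row. The list is also described as not final. These are points to verify.

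It is also an inference that the specialist will work from the worded definition. The G0 form shown asks only for estimated time, and the G1/G2 breast cancer form is not shown in the text.

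**Conclusion.** The defect stands. The P2 condition of BC2 contradicts the metric as worded in section 3.2.1, the synopsis and the G0 form. With the operator read as `>=` or `>` and one radiotherapy time per patient, the consolidated BC2 is 0% whatever the true delays, against about 11% to 52% under the assumed shares. With `<=` it would be 100%. Either way ABC2, ACC2 and the G1-to-G2 change in ACC2 carry no information on curation quality, and the BC2 part of H2-BC could fail or pass for the wrong reason. This assumes that the query is run as specified and that the specialist answers the worded question. One of the three queries is affected. The correction is needed before BC2 is used, because no later analysis can recover the intended interval from an answer that ignores the surgery date.

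**What to change.** 1. In P2 of BC2, replace the right-hand operand by the time of 392090004 Operation on breast + 8 weeks.
2. Align the operator with the worded `>`, so that a gap of exactly 8 weeks is treated the same in words and code.
3. Before use, run BC1, BC2 and BC3 on a small synthetic set with known answers. Include gaps of 55, 56 and 57 days and a patient with two radiotherapy records.
4. If G1 has been run, recompute its BC2 and ACC2 with the corrected query. Section 4.4.2 provides for deleting the patient data after the evaluation report, so this should be done while the records are held.
5. Check the original table of section 10.5 on three points: that an adjuvant radiotherapy start date is available for BC2; that 428923005, used in BC1, is listed; and that BC1 does not count 445232009 where it is recorded with the Elective qualifier for fractions to elective regions.

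The cost is one operand and one operator, a short test run, and a check of a few registry rows. Further edits to section 10.5 are needed only if that check finds a gap.
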